7.1. Clinical investigation-related procedures

Screening Visit (V0), Day 0:

- Introduction to the investigation and review of Subject information Form
- Check of in- and exclusion criteria
- Informed Consent Form – ICF signed at Visit 0. If subject wishes to have time for consideration, it is possible and the ICF is signed at Visit 1 the following day
- Inclusion in investigation and allocation of subject number after ICF is signed

Baseline Visit (V1), Day 1:

- Introduction to the investigation and review of Subject information Form
- ICF signed (if not signed at Visit 0)
- Confirmation of inclusion and exclusion criteria if more than 24 hours has passed since Visit 0
- Collect baseline information:
 - Gender (male/female)
 - Age (at time of enrollment (years)
 - Height (cm)
 - Weight (kg)
 - Urinary incontinence (Y/N)
 - Faecal incontinence (Y/N)
 - Date and main reason for admission (e.g., diabetes mellitus, cardiovascular disease, renal disease, pulmonary disease, anaemia, trauma, other)
 - Skin inspection
 - Braden Scale Score
- Apply Biatain Silicone Bandage on the sacral area

Baseline 2-7, skin inspection, Day 2-7:

- Partial lift of test product and skin inspection for signs of non-blanchable erythema over bony prominence/sacral pressure injury over bony prominence

- Re-application of the test product
- Has there been a test product change (Y/N)?
 - if yes, please register what the cause of the change was (dressing soilage, weakened border, damp/saturated dressing, bulky foam, other)

Termination Visit 8, Day 8 or at the day of discharge/earlier termination date:

- Have signs of non-blanchable erythema over bony prominence/sacral pressure injury over bony prominence developed (Y/N)?
 - If yes, please specify stage of pressure injury (*Appendix 3*)
- Was there any non-compliance to the local pressure injury prevention guideline (Y/N)?
 - If yes, explain non-compliance
 - if yes, please include a summary in the comment page

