10.2. Sample size

A sample size of 67 subjects will be enrolled with a minimum of 50 completers. This number is assessed to be sufficient to evaluate safety of the product.

The exploratory purpose of the investigation is to estimate the proportion of hospital-acquired pressure injuries in hospital-admitted patients with a 95% confidence interval. The confidence interval is then to be compared with the confidence interval of the results found by Mölnlycke. In the Mölnlycke investigation, the incidence in the control group was estimated to 5.3% [2.3%; 10.1%]³. 50 completing subjects will give a power of more than 80% to show an upper 95% confidence limit of 7.2% or less. This calculation assumes, that the true incidence rate for Biatain Silicone Sacral is 1.2% as we expect it to be as good as the intervention group in the Mölnlycke investigation³. It is further assumed that the confidence interval will be estimated as an exact confidence interval for binomial proportions. The precision of the estimated rate and the chosen sample size is evaluated to be sufficient to draw comparative conclusions between the rate of hospital-acquired sacral pressure injuries found in the suggested observational investigation and rates of hospital-acquired pressure injuries reported in literature.

To account for an estimated drop-out rate of 30%, 67 subjects must be enrolled to assure, that 50 subjects will complete the investigation.

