10.3. Level of significance and power

A two-sided significance level of 5% will be applied. For a description of the power see section 10.2 above.

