18.2. Adverse device effect

An adverse event, which is related to the use of the investigational medical device, is an adverse device effect, and should be marked as unlikely related, possible related, probable related or with causal relationship on the adverse event form.

The definition of an adverse device effect includes any event resulting from insufficiencies or inadequacies in the instruction for use, deployment, implantation, installation and operation, or any malfunction of the medical device, as well as any event resulting from use error or from intentional misuse of the device.

Table 6 lists anticipated adverse device effects that may occur, based on the IFU and their likely incidence rates based on adverse events reported in clinical studies⁴.

Table 6

ANTICIPATED ADE	INCIDENCE RATES
Local pressure injury/Erythema*	1-10%
Skin irritation/inflammation/itching	0.1 %-1%
Maceration and/or local fungus infection of the skin	0.01-0.1%
Pain	0.01-0.1%
Blistering	0.01-0.1%
Allergic skin reaction	Not known

* *Temporary redness/erythema upon removal of the sacral bandage is not considered an adverse device effect, however an abnormal development in intensity or duration should be considered as such.*

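### The precision claimed in section 10.2 rests on one borrowed rate of 1.2%, and is met neither at that rate nor anywhere in the 1-10% band of Table 6

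*Combined protocol and SAP*

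**What the plan says.** Section 10.2 states that "50 completing subjects will give a power of more than 80% to show an upper 95% confidence limit of 7.2% or less". The device's true rate is set by "This calculation assumes, that the true incidence rate for Biatain Silicone Sacral is 1.2" per cent, and the reason given is "as we expect it to be as good as the intervention group in the Mölnlycke investigation". The same section says that "the confidence interval will be estimated as an exact confidence interval for binomial proportions", and section 10.3 adds "A two-sided significance level of 5% will be applied". The reference is the control group of the cited trial, 5.3% with interval 2.3% to 10.1%. Section 10.2 then judges the precision and sample size good enough for comparisons with published rates, and section 10.4 requires the estimate to be comparable with that reference.

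Section 18.2, Table 6, lists "Local pressure injury/Erythema" as an anticipated adverse device effect at 1-10%. The table is said to rest on the instructions for use and on "their likely incidence rates based on adverse events reported in clinical studies", with a reference to the sponsor's clinical evaluation report. Section 10.2 does not mention it. The termination-visit item in section 7.1 also counts erythema of one kind (it reads "Have signs of non-blanchable erythema over bony prominence/sacral pressure injury over bony prominence developed (Y/N").

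**The concern.** The precision statement depends on one value, which is an expectation carried over from a different dressing. The title of the cited trial places it in trauma and critically ill patients, whereas this study enrols a range of ward patients with Braden scores of 6 to 18. With 50 completers and an event this rare, the result turns on whether zero, one or two injuries occur. The upper limit is therefore very sensitive to the assumed rate. A reader of section 10.2 sees neither that sensitivity nor whether the stated power follows from the stated inputs.

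At stake is what may be concluded at the end. Section 10.2 prepares the reader for a comparison with literature rates. If the interval is likely to span the whole reference interval, the study cannot distinguish a rate like the reference control group's from a clearly lower one, and a report relying on section 10.2 would overstate what was shown.

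**Working it through.** **Inputs.** n = 50 completers, limit 7.2%, true rate p = 1.2%, exact binomial interval, reference interval 2.3-10.1% (all section 10.2); two-sided 5% (section 10.3); illustrative band 1-10% (Table 6, section 18.2).

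**Step 1: which results meet the limit.** Exact (Clopper-Pearson) two-sided 95% intervals for x events in 50:

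| x | Lower | Upper |
|---|---|---|
| 0 | 0% | 7.11% |
| 1 | 0.05% | 10.65% |
| 2 | 0.49% | 13.71% |
| 3 | 1.26% | 16.55% |
| 4 | 2.22% | 19.23% |
| 5 | 3.33% | 21.81% |

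For x = 0 the upper limit is 1 − 0.025^(1/50) = 7.11%. Only x = 0 gives 7.2% or less.

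**Step 2: the plan's own figure.** Power = P(X = 0) = (1 − p)^50 = 0.988^50 = 54.7%, against the stated more than 80%. The figure is not reproduced. With n = 50, a one-sided exact limit, a Wilson interval and a mid-P interval also admit only x = 0 and give 54.7%. A Wald interval admits x = 1 (upper limit 5.88%) and gives P(X ≤ 1) = 87.9%, but the plan specifies an exact interval. Counting all 67 enrolled does not help: 1/67 has an upper limit of 8.04%, so zero events are still needed and 0.988^67 = 44.5%. A one-sided exact limit with 67 would give 80.8%, but the plan states 50 completers and a two-sided level. Where the stated figure came from cannot be determined from the documents.

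**Step 3: the rate that the claim needs.** (1 − p)^50 ≥ 0.80 requires p ≤ 1 − 0.80^(1/50) = 0.445%.

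**Step 4: other rates.** Expected events = 50p. The mean upper limit is the average of the exact upper limit over Binomial(50, p).

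| True rate | Expected events | Mean upper limit | Chance of 7.2% or less |
|---|---|---|---|
| 1% | 0.5 | 8.8% | 60.5% |
| 1.2% | 0.6 | 9.2% | 54.7% |
| 3% | 1.5 | 12.0% | 21.8% |
| 5% | 2.5 | 14.9% | 7.7% |
| 10% | 5 | 21.6% | 0.5% |

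**Step 5: what the interval can separate.** From step 1, the intervals for x = 1 to 4 all start below 2.3% and end above 10.1%, so each contains the whole reference interval. The probability is P(X ≤ 4) − P(X = 0):

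- at 1.2%: 99.97% − 54.68% = 45%
- at 3%: 98.32% − 21.81% = 77%
- at 5%: 89.64% − 7.69% = 82%

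Even the best result, 0/50, gives 0 to 7.11%, which still includes the reference estimate of 5.3%.

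**The case against.** The plan states 1.2%, its source and its reason openly. Borrowing a planning rate from a trial of a similar dressing is common practice and not an error in itself. The endpoint is exploratory, section 10.4 sets no formal success criterion for safety, and section 10.2 judges the sample size adequate for safety without using this calculation. All of that stands, and it is why the remedy is limited to wording and a table.

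A reader might infer that the sponsor's own Table 6 shows 1.2% to be wrong for this device. The documents do not support that. The value 1.2% lies inside the 1-10% band. The row is a composite of adverse device effects, whereas the endpoint counts sacral injury whatever its cause. The overlap is real, because non-blanchable erythema counts towards the endpoint, but partial: the table's footnote concerns erythema that is abnormal in intensity or duration after removal of the dressing. The text does not say which products supplied the rates. Several rows are tenfold bands, which look like frequency categories, so 3%, 5% and 10% are not sponsor estimates of the endpoint rate.

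A reader might also infer that the planned precision holds at the floor of the band. It does not: the chance at 1% is 60.5%.

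Finally, it can be said that the main defect is arithmetic, since the claim already fails at 1.2%. That is correct. But replacing the power figure alone would still hide how quickly the chance falls at higher rates.

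**Conclusion.** The point holds in this form. The claim of more than 80% power is not met at the plan's own 1.2% (54.7%) or at any rate from 1% to 10% (60.5% falling to 0.5%). It would need a true rate of about 0.445% or less. At 1.2% there is a 45% chance that the interval swallows the whole reference interval, so the assurance about comparative conclusions is unsupported even before the borrowed rate is questioned. The single unexamined rate then conceals how much worse matters become if the truth is higher.

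This rests on 50 completers, an exact two-sided 95% interval and independent subjects, the first two as the plan specifies. The Table 6 band serves only to show sensitivity; it is not evidence that the true rate exceeds 1.2%. The consequence is confined to the exploratory endpoint and to the comparability statement in section 10.4.

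**What to change.** In section 10.2:

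1. Replace the more-than-80% figure by 54.7% at a true rate of 1.2%.
2. Add the step 4 table (expected events, mean exact upper limit and chance of an upper limit of 7.2% or less at 1%, 1.2%, 3%, 5% and 10%). Label it illustrative, because Table 6 is not a direct estimate of the endpoint rate.
3. State that, with 50 completers, 7.2% is reached only if no injury is observed.
4. Reword the sentence on sufficiency to say that the comparison with literature rates is descriptive.

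The cost is a five-row table and a few sentences. Enrolment, endpoints and analysis stay as they are. The downside for the sponsor is a less favourable stated precision.

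### Section 10.2 claims enough precision for comparative conclusions, but with up to 67 analysed subjects even zero injuries leaves the 5.3% reference rate inside the planned 95% interval

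*Combined protocol and SAP*

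**What the plan says.** The claim is in section 10.2: "The precision of the estimated rate and the chosen sample size is evaluated to be sufficient to draw comparative conclusions" between the rate found here and rates reported in the literature. The surrounding text supplies these elements:

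- **Size.** "A sample size of 67 subjects will be enrolled with a minimum of 50 completers".
- **Reference.** The control group of the cited randomised trial of a multi-layer foam dressing, at 5.3% with interval 2.3% to 10.1%. Section 10.4 repeats these figures and asks that the study's result be comparable to them, with no numerical rule.
- **Assumption for the device.** "the true incidence rate for Biatain Silicone Sacral is 1.2"%.
- **Precision target.** "50 completing subjects will give a power of more than 80% to show an upper 95% confidence limit of 7.2% or less".
- **Interval method.** "the confidence interval will be estimated as an exact confidence interval for binomial proportions".
- **Comparison.** "The confidence interval is then to be compared with the confidence interval of the results found by Mölnlycke".
- **Level (section 10.3).** "A two-sided significance level of 5% will be applied".

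The endpoint, sacral pressure injury yes/no, is exploratory (section 5.4). The primary endpoint is the number of adverse events (section 5.2).

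**The concern.** The sufficiency statement can be tested before any data exist. With an exact binomial interval, the most favourable result is zero injuries, and its upper limit depends only on the number analysed. If that limit is above the reference rate, no favourable result at that size excludes the reference, however well the dressing performs.

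The plan assumes 1.2% for the device and quotes 5.3% for the control group, so a reader will take comparative conclusions to include telling these two rates apart. A zero-injury result could then be reported as comparative evidence of a lower rate when the plan's own interval does not support it. Section 21.1 reserves use of the data for regulatory and reimbursement purposes, so the wording matters outside the study report.

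**Working it through.** **Inputs.** n = 50 (minimum completers) and n = 67 (enrolled), from section 10.2. Exact binomial interval, from section 10.2. Two-sided 5%, from section 10.3, so 2.5% in each tail. Reference 5.3% [2.3%; 10.1%] and assumed device rate 1.2%, from section 10.2.

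**Step 1: the plan's own target.** For zero events the exact upper limit is 1 − 0.025^(1/n).

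- 0/50: 1 − 0.025^(1/50) = 1 − 0.92888 = 7.11%.
- 1/50: 10.65% (beta quantile).

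The 7.2% target is thus the limit for zero events, rounded up. Only 0/50 meets it, so the probability of meeting it at a true rate of 1.2% is 0.988^50 = 54.7%. The stated power of more than 80% does not reproduce. That is a separate error, and the present point does not depend on it.

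**Step 2: best attainable limits against 5.3%.**

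| Result | Exact 95% interval | Excludes 5.3%? |
|---|---|---|
| 0/50 | 0 to 7.11% | No |
| 0/67 | 0 to 5.36% | No |
| 0/68 | 0 to 5.28% | Yes, barely |

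The number needed with zero events is ln(0.025)/ln(1 − 0.053) = 67.7, so 68. The 7.2% target is 1.9 points above 5.3% (7.2 − 5.3), so meeting it in full would still not show a lower rate.

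**Step 3: the planned interval-beside-interval comparison at n = 50.**

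- Favourable side: the upper limit would have to fall below 2.3%. With zero events this needs ln(0.025)/ln(1 − 0.023) = 158.5, so 159 completers.
- Unfavourable side: the lower limit would have to exceed 10.1%. At 10/50 it is 10.03% (overlap); at 11/50 it is 11.53% (separation).

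Every result from 0/50 to 10/50, that is 0% to 20%, overlaps the reference interval.

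**Step 4: allowing for uncertainty in the reference.** The documents do not give the reference counts. A search over n from 20 to 399 finds only 8/152 reproducing the quoted figures: 5.26%, exact interval 2.30% to 10.11%. Taking 8/152 as an assumption, the Newcombe interval for the difference uses Wilson limits. These are z²/(n + z²) for zero events (3.84/53.84 = 7.13% at n = 50; 3.84/70.84 = 5.42% at n = 67) and 2.69% to 10.04% for 8/152. The upper ends, in percentage points, are:

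- 0/50: −5.26 + √(7.13² + (5.26 − 2.69)²) = −5.26 + 7.58 = +2.3. The interval is −10.0 to +2.3; Fisher two-sided p = 0.20.
- 0/67: −5.26 + √(5.42² + 2.57²) = −5.26 + 6.00 = +0.7. The interval is −10.0 to +0.7; Fisher two-sided p = 0.11.

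Both include zero, so the conclusion does not depend on treating 5.3% as a fixed value.

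**The case against.** Several objections deserve weight.

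**The size is not capped at 67.** Section 6.4 lets subjects already informed when the target is reached still enter. Section 6.5 calls for replacement if more than 17 drop out, although it also says that withdrawn subjects are not replaced. Section 10.1 bases the exploratory analysis on the ITT population but computes the proportion among completed subjects. The shortfall at 0/67 is only 0.06 points, and 0/68 gives 5.28%. A reader might infer that no possible result could ever show a lower rate. The documents do not support that, and the conclusion must be tied to 67 or fewer analysed subjects. At the planned 50 the gap is 1.8 points (7.11 − 5.3) and is not marginal.

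**The plan sets no requirement that the limit fall below 5.3%.** It states a 7.2% target and asks for comparability. This stands, and it is why the finding is about the sufficiency claim and not about a failed criterion. Still, 5.3% is the only reference rate given, and the comparison the plan does name, interval against interval, is harder to pass favourably.

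**Comparative conclusions can be unfavourable, and other rates may be used.** At 7/50 the lower limit is 5.82%, above 5.3%; at 11/50 the whole interval lies above the reference interval. The synopsis also names global, European and Scandinavian proportions without giving values, and 0/50 would exclude any fixed rate above 7.11%. A reader might infer that the sufficiency claim is false whatever the true rate is. That goes too far: it fails for showing a rate lower than the quoted reference, and cannot be judged for rates the documents do not state.

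**Section 10.3.** A reader might infer that the 5% level is attached to nothing. It can be read as setting the confidence level of the interval in section 10.1, and the plan promises no hypothesis test.

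**Conclusion.** The concern holds in a limited form. With up to 67 analysed subjects and the planned exact two-sided 95% interval, the study cannot show a rate below the 5.3% reference estimate: the lowest attainable upper limit is 7.11% at 50 and 5.36% at 67. The overlap comparison does not distinguish 0% from 20% at 50 completers. Section 10.2 therefore claims, in the favourable direction and against its only quoted reference, a precision that the planned size does not give.

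This rests on the exact two-sided method that the plan fixes. Other choices move the limit: a one-sided 95% limit at 0/67 is 4.37%, and a Jeffreys limit at 0/50 is 4.88%. The difference intervals rest on the inferred 8/152. The point should be corrected, but its weight is moderate, because the endpoint is exploratory and the safety objective is unaffected.

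**What to change.** In section 10.2, replace the sufficiency sentence with:

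> With 50 completers the narrowest attainable 95% interval is 0–7.1% (0–5.4% with 67); at these sizes the study is not able to show a rate below the 5.3% reference estimate, and comparison with literature rates is descriptive.

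Replace the interval-beside-interval comparison with a 95% confidence interval for the difference in proportions against the cited trial's control group, labelled descriptive. Take the event counts from the cited trial report; the sponsor must confirm them, since 8/152 is only inferred here from the quoted rate and interval.

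The cost is a change of wording in section 10.2 and one extra interval in the analysis. No more patients and no change in conduct are needed. The sponsor gives up a more favourable statement about what a zero-injury result would show.

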During the study period, data will be collected to determine a *proportion of hospital acquired pressure injuries in hospital admitted patients with a limited level of mobility*. The study is designed as a non-comparative, single-arm, prospective multi-center observational study. The study will be conducted in Danish hospitals and the establish proportion of hospital-acquired pressure injuries will be compared to global, European, and Scandinavian proportions of hospital-acquired pressure injuries reported in literature.

(The investigation is a non-comparative, single-arm investigation with one test period. In total 67 hospital-admitted patients will be included. Each subject will have daily test-visits overseen by the Principal Investigator

or designee during an expected 7-day test period in total or until the subject is discharged. The subjects will test the CE marked test product Biatain Silicone Sacral 15 cm x 19 cm / 6 in x 5.5 in).

Expected duration of the clinical investigation:

The investigation will be conducted from August 2022 through December 2022.

Primary endpoint:

Number of Adverse Events

Secondary endpoint:

Number of Device Deficiencies

Exploratory endpoint:

Hospital-acquired sacral pressure injuries during investigation period (Yes/No)

Population/subjects:

The subjects to be included in the study will be a range of partially immobilized hospital-admitted patients (from e.g., medical, surgical, lung and orthopedic surgical units) with a Braden score of 6-18.

(Hospital-admitted patients with a limited level of mobility and a Braden score between 6-18).

Inclusion and Exclusion Criteria:

Inclusion criteria	Exclusion criteria
Hospital-admitted patients at risk of developing a pressure injury with an expected hospital-stay of more than 24 hours from time of screening	Suspected or actual spinal injury precluding the patient from being turned
≥18 years of age and has full legal capacity	Sacral erythema, sacral pressure marks, pre-existing sacral pressure injury
Has given written consent to participate by signing the Informed Consent signature Form	Trauma to sacrum.
Has a Braden score of 6-18 at screening (within the last 24 hours or at time of screening) (Appendix 2)	Topical treatment with steroid cream in the sacral area. (treatment must have been terminated at least 14 days prior to enrollment)

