3.1. Aim and Objective

The aim of the clinical investigation is to evaluate safety of Biatain Silicone, when used as prophylactic prevention on hospital-admitted patients at risk of developing a pressure injury.

- **Primary objective:** Evaluate safety

- **Exploratory objective:** Establish the proportion of subjects, that develop pressure injuries during hospitalization while wearing Biatain Silicone Sacral

[figure not shown]
The proportion of hospital-acquired pressure injuries will be compared to relevant existing proportions in literature³.

4. Investigational device and comparator(s)

The Biatain Silicone Sacral product is a sterile pouch-packed, single use polyurethane foam dressings with silicone adhesive intended for wound management and can be used as part of a prophylactic therapy to help prevent skin damage e.g., pressure injuries.

The Biatain Silicone Sacral and dressings are available in different shapes to fit the sacral area of the body. In this investigation it will primarily be the heart-shaped product, which will be used. However, if needed the diamond shaped, can be chosen.

**Biatain Silicone Sacral,
item no. 39001**

**Biatain Silicone Sacral,
item no. 39000**

Figure 1: Biatain Silicone Sacral dressings.

The two Biatain Silicone Sacral dressings consist of the same five layers:

- Polyurethane (PU) top film – a permeable barrier film of PU that is printed with dots
- Tissue layer – a tissue layer of cellulose fibres
- Super absorber layer – a cellulose fibre matrix with super absorbing particles
- Biatain foam pad – a PU foam with a thickness of 2.3 mm
- Silicone adhesive bi-layer – a silicone adhesive gel

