5.1. General

The Clinical investigation is an open-labelled, non-comparative, single-arm, prospective, multi-center observational investigation.

Subjects will be applied Biatain Silicone Sacral dressing in the sacral area at Baseline Visit / V1 in a test period up to 7 days or until discharged.

In total, 67 hospital-admitted patients will be enrolled. Each subject will have a screening visit (V0/Day 0), a Baseline visit (V1/Day1) and daily visits (V2/Day2 to V8/termination visit) performed. If the subject is discharged prior to visit 8, the termination visit will be performed at the day of the discharge.

All visits will be carried out by the Principal Investigator or delegate.

Before scheduling V0 the subject will be informed about the investigation, where the PI or delegate will give a detailed information about the requirements, the content and what it involves participating in the investigation. See section 6.4 for recruitment.

Screening visit (V0/Day0) and Baseline visit (V1/Day1) can be performed the same day. If the subject wishes to re-consider his or her participation after Screening (Visit0/Day0), the subject has the right to wait minimum 24 hours before decision to participate. If the subject hereafter decides to participate in the clinical investigation, Baseline visit (V1/Day1) will be scheduled, and the inclusion procedures will be performed. Screening visit/V0 and baseline visit must be performed on following days unless performed the same day.

[figure not shown]

Figure 2: Study Design CP346

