5.4. Exploratory endpoint

Hospital-acquired sacral pressure injuries during investigation period (Yes/No)

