6.2. Inclusion criteria and Exclusion criteria

Inclusion criteria	Justification for inclusion criteria
Hospital-admitted patients at risk of developing a pressure injury with an expected hospital-stay of more than 24 hours from visit 1	Intended patient population
≥18 years of age and has full legal capacity	To meet the Helsinki declaration
Has given written consent to participate by signing the Informed Consent signature Form	To meet the Helsinki declaration
Has a Braden score of 6-18 at screening (performed within the last 24 hours) (Appendix 2)	To meet primary endpoint
Intact sacral skin (non-breached skin, without signs of non-blanchable erythema over bony prominence/pre-existing sacral pressure injury over bony prominence) (Appendix 3)	Skin must be intact on admission to detect developing pressure injuries during investigation period

Table 2. Inclusion criteria

Exclusion criteria	Justification for exclusion criteria
Suspected or actual spinal injury precluding the patient from being turned	Turning of the patient (to mobilize them) at regular intervals are a part of standard procedure for pressure injury prevention
Sacral erythema, sacral pressure marks, pre-existing sacral pressure injury	Skin must be intact on admission to detect developing pressure injuries during investigation period
Trauma to sacrum	Skin must be intact on admission to detect developing pressure injuries during investigation period.
Topical treatment with steroid creme in the sacral area (treatment must have been terminated at least 14 days prior to enrollment)	Steroid creme may interfere with the skin condition and make it more fragile
Pregnancy or breastfeeding	Even though the ingredients and recipes have been approved for human beings, their effect on embryos, fetuses and infants are unknown

Table 3. Exclusion criteria

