10.1. Statistical design, method and analytical procedures

Definition of analysis populations

Safety populations and Intention to Treat (ITT) will be defined at a formal data review meeting before database lock. As a minimum, the data manager, the clinical manager and the statistician will be involved in the classification of subjects.

The safety population will be constituted by all subjects with valid informed consent. The ITT population (full analysis set) will be constituted by all subjects with valid informed consent, who have been exposed to the Test Product, with information on at least one endpoint.

The summary of the primary and secondary endpoints will be based upon the safety population, whereas the statistical analysis of the exploratory endpoint will be based on the ITT population. Invalid individual data points may be omitted from analysis even though the corresponding subject is part of the ITT population. Any exclusion of data points will be documented.

A formal per protocol (PP) population is not planned due to the explorative nature of the investigation. Considering the data obtained it might be considered to make additional explorative analyses based on a subset of the ITT population.

Analysis of the endpoints and baseline data.

The endpoints as well as baseline assessments will be listed and summarized by descriptive statistics. The summaries will be made for relevant visits (baseline or V1-V8), separately.

Summary statistics for continuous variables are presented with N, Mean, SD (standard deviation), Median, Min and Max, where N denotes the number of subjects contributing with non-missing data. For discrete variables, summary statistics are presented with N and percentage, where percentage is based on the total number of subjects/observations with non-missing data.

The incidence rate (proportion) of hospital-acquired pressure injuries in hospital-admitted patients will be estimated based on the exploratory endpoint (pressure injuries: Yes/No). The proportion of completed subjects answering "Yes" will be calculated. By use of an exact test in the Binomial distribution a 95% confidence interval will be estimated for the proportion.

All statistical analysis will be performed with SAS (version 9.4/Enterprise Guide version 7.1).

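### A sacral-only count from V1 to at most Day 8 is to be compared with literature rates of hospital-acquired pressure injuries that the plan does not require to match on site, category or observation window

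*Combined protocol and SAP*

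**What the plan says.** The endpoint in section 5.4 is "Hospital-acquired sacral pressure injuries during investigation period (Yes/No". The procedures follow it. Section 7.1 has the dressing partly lifted for skin inspection on Days 2 to 7, and Table 5 names the skin inspected as sacral. The termination question in 7.1 counts non-blanchable erythema, which is Category I in Appendix 3. Observation starts when the dressing is applied at V1 and runs "in a test period up to 7 days or until discharged"; the last assessment is "Termination Visit 8, Day 8 or at the day of discharge/earlier termination date".

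The target and the benchmarks are worded more widely:

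- The exploratory objective in 3.1 is to "Establish the proportion of subjects, that develop pressure injuries during hospitalization while wearing Biatain Silicone Sacral", with no site named.
- Section 10.1: "The incidence rate (proportion) of hospital-acquired pressure injuries in hospital-admitted patients will be estimated based on the exploratory endpoint (pressure injuries: Yes/No". Again no site is named.
- Section 10.2 regards the planned number of subjects as large enough to support a comparison, and words the two sides of it as follows: "between the rate of hospital-acquired sacral pressure injuries found in the suggested observational investigation and rates of hospital-acquired pressure injuries reported in literature". The word sacral stands on one side only.
- The synopsis, under the design of the investigation, says the proportion will be "compared to global, European, and Scandinavian proportions of hospital-acquired pressure injuries reported in literature".
- Section 10.4 requires the estimate and its interval to be comparable to 5.3% [2.3%; 10.1%]. Neither 10.2 nor 10.4 gives the site, minimum category or follow-up behind that figure. The title in the bibliography shows that the cited trial covered sacral and heel ulcers in trauma and critically ill patients.

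On the start of observation, section 6.2 justifies the skin criteria with "Skin must be intact on admission to detect developing pressure injuries during investigation period". Eligibility, however, is checked at V0 and V1, candidates are found among patients already admitted (6.4), and no limit is set on days since admission.

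**The concern.** A sacral count is a subset of an any-site count. Set against an any-site rate, the study proportion is lower for a reason unrelated to the dressing. The time window can act the same way. A sacral injury acquired in hospital before V1 makes the patient ineligible, and one arising after Day 8 is not seen. If a literature figure includes such injuries, the study figure is again lower by definition.

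Section 5.5 says this endpoint was chosen to examine whether the dressing helps to prevent pressure injuries. Section 2 says the study is meant to support that use, and 21.1 reserves the data for regulatory and reimbursement purposes. A favourable comparison that partly reflects a difference in definition could therefore be used as evidence of performance.

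**Working it through.** **1. The plan's own figures.** The benchmark interval reproduces: 8/152 = 5.3%, with exact 95% limits 2.3% and 10.1%. The power statement in 10.2 does not. With 50 completers, the exact two-sided upper limit is 7.11% for 0 events and 10.65% for 1 event, so only 0 events meets the 7.2% target. At a true rate of 1.2% that has probability 0.988^50 = 54.7%, against the stated figure of more than 80%. This is a separate matter, and the present point does not rest on it.

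**2. Scope, side by side.**

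| | Study proportion | Literature rates (synopsis, 10.2) | Named 5.3% |
|---|---|---|---|
| Site | Sacrum | Not restricted | Not stated; trial title names sacrum and heel |
| Minimum category | Category I | Not stated | Not stated |
| Start | V1, any day of stay | Not stated | Not stated |
| End | Day 8 or discharge | Not stated | Not stated |
| Population | Hospital-admitted, Braden 6-18 | Not restricted | Trauma and critically ill |

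No section requires any row to match.

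**3. Size of the site mismatch, for illustration.** The documents give neither a sacral share nor an any-site rate. Assume an any-site rate of 10% and a sacral share of 30% to 60%. An inert dressing then has an expected sacral rate of:

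- 10% x 0.30 = 3%
- 10% x 0.60 = 6%

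The apparent relative reduction is 1 - 0.60 = 40% to 1 - 0.30 = 70%, from the site definition alone.

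With 50 completers, the point estimate is below 10% when there are at most 4 events. The whole exact interval is below 10% only with 0 events, since the upper limits are 7.11% for 0 and 10.65% for 1. For an inert dressing:

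| True rate | Expected events | P(at most 4 events) | P(0 events) = (1 - rate)^50 |
|---|---|---|---|
| 10% (no mismatch) | 5.0 | 43% | 0.90^50 = 0.5% |
| 6% | 3.0 | 82% | 0.94^50 = 4.5% |
| 3% | 1.5 | 98% | 0.97^50 = 21.8% |

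The mismatch acts mainly on the point estimate. These figures isolate the site effect and leave out every other difference between the study and the literature.

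**4. The named benchmark.** The conversion in step 3 should not be applied to 5.3%, because the documents do not say that 5.3% is an any-site rate. Two facts hold whatever its site:

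- The upper limit for 0/50 is 1 - 0.025^(1/50) = 7.11%, so the exact interval cannot lie below 5.3%. For 0/67 it is 1 - 0.025^(1/67) = 5.36%, still above. It would take 68 subjects with no event.
- If the comparability criterion in 10.4 is read as overlap of intervals, an inert dressing with a true rate of exactly 5.3% meets it with probability above 99.9%. Passing in that sense does not depend on any mismatch.

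**The case against.** The strongest reply is that the plan is loosely worded rather than wrong. Section 10.1 estimates the rate from the exploratory endpoint, which is defined as sacral. The objective is limited to the time the dressing is worn, which largely settles its time scope. Section 3.1 speaks of relevant literature proportions and cites only the one trial. A heel injury is not lost altogether: it meets the adverse event definition in 18.1 and would count in the primary endpoint. The endpoint is exploratory, and 10.4 asks for comparability, not a lower rate.

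Most of this stands, and it narrows the point. It does not remove it, because 10.2 itself sets a sacral rate against rates with no site restriction, the synopsis names broad regional proportions, and nothing says what makes a literature rate relevant.

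A reader might infer something stronger: that even an inert dressing would look preventive, so that the objective is answered in the product's favour by construction. The documents do not support that. Enrolment is limited to Braden scores of 6-18, skin is inspected daily and Category I counts; each may raise the observed proportion relative to broad hospital figures. Excluding injuries present before V1 biases the comparison only if the literature figures include such injuries, which cannot be seen here.

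**Conclusion.** The mismatch is in the text and holds with high confidence: a sacral, V1-to-Day-8 proportion is to be compared with literature rates not restricted by site or window, and no matching is required. Where a literature rate is wider in scope, this component favours the dressing regardless of any effect. Its possible size is shown only under assumptions: with a sacral share of 30% to 60%, an any-site 10% becomes 3% to 6%. The net direction across all differences is not established. Against 5.3%, bias is possible but not shown, and any favourable appearance could be in the point estimate only. Since the endpoint is exploratory, this should be corrected, but it does not undermine the primary safety objective.

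**What to change.** 1. In 3.1, 10.1, 10.2, 10.4 and the synopsis, name one quantity: the proportion of subjects with a new sacral pressure injury (Category I or higher) between application at V1 and V8 or discharge.
2. State the site, minimum category and follow-up behind 5.3% [2.3%; 10.1%].
3. Before database lock, list the literature rates that match on sacral site and minimum category, and as far as possible on observation window and population. Limit comparative conclusions to these, and show unmatched rates as context only.
4. Report days from admission to V1 descriptively, using the admission date already collected at V1. Splitting the proportion by early and late enrolment would add almost nothing: 50 completers give about 50 x 1.2% = 0.6 to 50 x 5.3% = 2.65 expected events in total.

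The cost is wording, one short list of literature rates and one descriptive line; no new data are needed. The downside is that fewer literature figures will qualify and the comparison may look less favourable.
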